Intracranial hemorrhage	I60, I61, I62, I690, I691, I692, S064, S065, S066, S068	Diagnosis code + admission code + brain CT or MRI code *Brain CT or MRI: CT: HA441, HA451, HA461, HA471, HA851

		MRI: HE101, HE102, HE135, HE201, HE202, HE235, HE301, HE302, HE401, HE402, HE501, HE502, HE535
GI bleeding	I850, I983, K2211, K226, K228, K250, K252, K254, K256, K260, K262, K264, K266, K270, K272, K274, K276, K280, K282, K284, K286, K290, K3181, K5521, K625, K920, K921, K922	Diagnosis code + admission code
Other bleeding	D62, H448, H3572, H356, H313, H210, H113, H052, H470, H431, I312, N020-N029, N421, N831, N857, N920, N923, N930, N938, N939, M250, R233, R040, R041, R042, R048, R049, T792, T810, N950, R310, R311, R318, R58, T455, Y442, D683	Diagnosis code + admission code

- The earliest date of diagnosis of the major bleeding event after the index date will be defined as the outcome occurrence date.
- Patients will be followed up from the index date to the occurrence of an outcome, treatment discontinuation (30-day grace period), switch to another anticoagulants, in-hospital death, or end of the study period (31 Dec 2019) whichever comes first.

Potential Confounder(s)

- Sociodemographic characteristics such as age, sex, and index year will be assessed at the index date.
- CCI [23] and HAS-BLED [24] scores will be measured within the 6-month period prior to the index date.
- Initial presentation of VTE
 - DVT (I80.2, I80.3)
 - PE (I26.0, I26.9)
 - Both DVT and PE
- Comorbidities (ICD-10 diagnostic code) will be measured within the 6-month period prior to the index date.

- Antiphospholipid syndrome (D68.6, I82.9): As diagnosis of antiphospholipid syndrome is usually made after VTE diagnosis with subsequent diagnostic procedures, its presence will be evaluated within the 6-month period after the index date.
 - Asthma (J45)
 - Cancer (C00-C97): History of cancer (non-active) will be evaluated within a lifetime prior to the index date.
 - Chronic obstructive pulmonary disease (COPD; J40-J44)
 - Chronic kidney disease (N18, N19)
 - Chronic liver disease (B18, B19, K70-K77)
 - Diabetes mellitus (E10-E14)
 - Fracture (S22, S32, S42, S52, S62, S72, S82, S92, T10, T12)
 - Heart failure (I50)
 - Hyperlipidemia (E78)
 - Hypertension (I10-I15)
 - Ischemic heart disease (I24, I25)
 - Myocardial infarction (I21)
 - Stroke (I60-I64, I69, G45)
 - Trauma (T79, T98, V01–V99, W11–W17, W50–W52, W64, X34–X39, Y01–Y04, Y30–Y32)

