8. RESEARCH METHODS

8.1. Study design

A retrospective, observational, nationwide population-based cohort study will be conducted to describe the treatment patterns of anticoagulation therapies prescribed to patients with VTE in South Korea, and assess the risk of major bleeding associated with apixaban and other NOACs use, as compared with warfarin, by using the Health Insurance Review and Assessment Service (HIRA) database from 1 Mar 2012 to 31 Dec 2019 (Figure 1).

Note: HIRA, Health Insurance and Review Assessment service; LMWH, low molecular weight heparin; NOAC, non-vitamin K antagonist; PAC, parenteral anticoagulants; VTE, venous thromboembolism; W, warfarin

[†]Record of active cancer is defined as first diagnosis of cancer with V code within the past 6 months of period prior to index date; or receiving anti-cancer treatment under cancer diagnosis with V code within the past 6-month period prior to index date.

[‡]Warfarin-based and NOAC-based include either PAC with warfarin/NOAC or warfarin/NOAC only

[figure not shown]
Figure 1. Study participants inclusion and exclusion criteria

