8.2. Study population

The study cohort will be defined as patients diagnosed with VTE between 1 Mar 2013 and 30 Jun 2019. The cohort entry will be defined as the date of incident VTE diagnosis. The index date will be defined as the date of first prescription for anticoagulants within 30 days after the index VTE event. The length of the exclusion assessment window will vary depending on the condition, from 12-months at minimum to anytime prior to index date. The following patients will be excluded: A record of VTE diagnosis within the 12-month period prior to the index VTE encounter, diagnosed with atrial fibrillation, atrial flutter, mechanical heart valve replacement or mitral stenosis anytime prior to index date, had a record of Inferior Vena Cava filter anytime prior to index date, received anticoagulatory therapy within the 12-month period prior to index VTE encounter to restrict to new users of anticoagulatory therapy, prescribed two different anticoagulants on the same index date to prevent exposure misclassification, had a record of pregnancy within the 9-month period prior to index date, and for the Phase II of the study only, had a record of active cancer within six months period prior to index date.

Baseline sociodemographic characteristics (e.g., age, sex) will be assessed on the index date, whereas clinical characteristics (comorbidities, previous use of medications, Charlson comorbidity index [CCI], HAS-BLED scores, initial presentation of VTE, number of outpatient visits) will be assessed in the 6-month period prior to the index date except when otherwise specified in section 8.4 *Variables* (Figure 2).

Within this study cohort, we will describe the treatment patterns of anticoagulants prescribed for VTE treatment throughout the period of follow-up, defined as the period from the index date to the end of the study period. Moreover, if feasible, we will also examine the risk of major bleeding overall and by site, associated with each NOAC use, as compared with warfarin.

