8.4. Variables

Exposure

- **Phase I of the study:** PAC (UFH [Anatomical Therapeutic Chemical [ATC] code: B01AB01], LMWH [B01AB04, B01AB05, B01AB06, B01AB12], VKA (warfarin [B01AA03]), NOACs (apixaban [B01AF02], rivaroxaban [B01AF01], edoxaban [B01AF03], dabigatran [B01AE07])
- **Phase II of the study:** Apixaban (B01AF02), Rivaroxaban (B01AF01), Edoxaban (B01AF03), Dabigatran (B01AE07), Warfarin (B01AA03)

Outcome(s)

- **Phase I of the study**

- Sociodemographic and clinical characteristics of patients with VTE who initiated anticoagulants.
- Utilization of different anticoagulants at treatment initiation. Patients will be classified based on their index anticoagulant treatment received within 30 days after being diagnosed with VTE.
- Treatment interruption from the index anticoagulant treatment, which will be defined as when a patient has a gap with no new treatment within 30 days of the estimated end of supply, but subsequently restarts the index treatment after this period.[1] The time to treatment interruption will be defined as the period from the index date to the date of treatment interruption.
- Treatment switching will be defined as a prescription of another anticoagulant therapy that is started after the treatment initiation of the index anticoagulant treatment and within 30 days after the estimated end of supply of the index anticoagulant drug (exposure to the new anticoagulant treatment must last for at least 30 days to be considered as a treatment switch). The time to treatment switch will be defined as the period from the index date to the date of treatment switch.

Exemption: As heparin can be initiated at acute stage of DVT/PE before clinical decision to use OAC, a switch from initial heparin treatment to an OAC within 2 weeks after heparin treatment initiation will not be considered a treatment switch.

- Treatment discontinuation (complete discontinuation; no reinitiation) will be defined as when a patient who ended their first continuous treatment episode with the index anticoagulant treatment without switching, and subsequently have no further prescriptions for that respective anticoagulant treatment during all available follow-up time. The time to treatment discontinuation will be defined as the period from the index date to the date of treatment discontinuation.
- Overall anticoagulant treatment duration will be defined as the time period from the index date to the earliest of treatment interruption, switch, or discontinuation.

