Cancer surgeries	Specified in 'cancer-related surgery' of section 8.3.2
Benign surgeries	R4123-R4129, R4421, R4430, R3975
Cancer-related event (active cancer)	C00-C97 (excluding non-melanoma skin cancer, C44) with V code (V011, V027, V193, V194)
Kidney function change	
Chronic kidney disease	N18, N19
Acute kidney injury	N17
Liver function change	
Liver disease	B15-B19, K70-K77
Abnormal liver function	R94.5, R74.0

- **Phase II of the study**

- Major bleeding will be defined using primary or secondary diagnosis codes according to the ICD-10 diagnostic codes shown in below table and classified by site (intracranial, gastrointestinal [GI], all others).

Major bleeding	ICD-10 diagnosis code	Diagnostic definition
Intracranial hemorrhage	I60, I61, I62, I690, I691, I692, S064, S065, S066, S068	Diagnosis code + admission code + brain CT or MRI code

		* Brain CT or MRI: CT: HA441, HA451, HA461, HA471, HA851 MRI: HE101, HE102, HE135, HE201, HE202, HE235, HE301, HE302, HE401, HE402, HE501, HE502, HE535
GI bleeding	I850, I983, K2211, K226, K228, K250, K252, K254, K256, K260, K262, K264, K266, K270, K272, K274, K276, K280, K282, K284, K286, K290, K3181, K5521, K625, K920, K921, K922	Diagnosis code + admission code
Other bleeding	D62, H448, H3572, H356, H313, H210, H113, H052, H470, H431, I312, N020-N029, N421, N831, N857, N920, N923, N930, N938, N939, M250, R233, R040, R041, R042, R048, R049, T792, T810, N950, R310, R311, R318, R58, T455, Y442, D683	Diagnosis code + admission code

- The earliest date of diagnosis of the major bleeding event after the index date will be defined as the outcome occurrence date.
- Patients will be followed up from the index date to the occurrence of an outcome, treatment discontinuation (30-day grace period), switch to another anticoagulants, in-hospital death, or end of the study period (31 Dec 2019) whichever comes first.

Potential Confounder(s)

- Sociodemographic characteristics such as age, sex, and index year will be assessed at the index date.
- CCI [2] and HAS-BLED [3] scores will be measured within the 6-month period prior to the index date.

List of CCI	Score	ICD-10 codes
Cerebrovascular disease	1	G45, G46, H34, I60-I69
Congestive heart failure	1	I09.9, I11.0, I13.0, I13.2, I25.5, I42.0, I42.5-I42.9, I43, I50, P29.0
Chronic pulmonary disease	1	I27.8, I27.9, J40-J47, J60-J67, J68.4, J70.1, J70.3

Dementia	1	F00–F03, F05.1, G30, G31.1

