10. STATISTICAL ANALYSIS

All statistical analyses will be performed using SAS Enterprise Guide 7.1 (SAS Institute Inc., Cary, NC, USA), provided by HIRA through a virtual access machine.

Phase I of the study (descriptive)

Main Analysis

- Descriptive analysis will be conducted separately in two cohorts of non-cancer VTE and cancer VTE patients according to co-presence of active cancer.
- Sociodemographic and clinical characteristics will be summarized with means (standard deviations [STD]) or median (interquartile range [IQR]) for continuous variables and with count (proportions) for categorical variables for the three treatment groups of interest: PAC only (UFH, LMWH, UFH+LMWH), warfarin-based (warfarin, PAC/warfarin) group, NOAC-based (NOAC, PAC/NOAC) group. NOAC-based (NOAC, only group, PAC/NOAC) group. Analysis of variance, and chi-square test will be conducted for continuous variables, and categorical variables, respectively.
 - In order to distinguish between PAC bridging therapy and PAC treatment, we will apply a time restriction of 2 weeks to PAC bridging therapy.
- Temporal trend in anticoagulation therapy for VTE will be presented between 1 Mar 2013 and 30 Jun 2019. Proportions of the index OACs will be estimated according to calendar year and quarter.
- The number and percentage of patients who discontinue treatment completely, experience treatment interruption and treatment switch during their follow-up will be described by the index anticoagulant treatment received. Results will be limited to the first of each of these events for each patient. For patients experiencing a treatment switch, the new treatment will be described at the time of their first switcher per individual drug.
- The duration of the index treatment by the index anticoagulant treatment received will also be summarized in terms of days using descriptive statistics (mean [STD], median [IQR]).
- The Kaplan-Meier method will be applied to derive the empirical distribution of time to each of the treatment endpoints of interest (e.g., treatment discontinuation or switch); these analyses will be performed per index anticoagulant treatment received and no comparisons will be made. Log-rank test will be conducted at the 3-, and 6 months after treatment initiation to assess statistical significance between the survival curves. Persistent rate will also be calculated at the same time point.

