- In the NOAC-based group, all analyses will be repeated stratified by each individual NOAC class (e.g, apixaban, dabigatran, rivaroxaban, edoxaban) to

PFIZER CONFIDENTIAL

identify the difference in baseline characteristics and treatment patterns between each NOAC class.

- To identify potential reasons for treatment change, clinical events preceding the first treatment change (major bleeding, thromboembolism diagnosis, complications of VTE, major surgery, active cancer, a new diagnosis of CKD or AKI, a new diagnosis of liver disease or abnormal liver function) will be measured within 30 days prior to the first date of treatment change. Patients can contribute with multiple events.
- All analyses of treatment patterns will be presented stratified according to the index anticoagulant treatment, and not overall or per drug class.

Phase II of the study (comparative)

Propensity score analysis

- To balance and adjust for any potential differences in baseline sociodemographic and clinical characteristics between treatment groups, propensity score (PS) methods will be implemented.
 - A logistic regression model will be used to estimate the predicted probability (propensity) of initiating each NOAC compared with warfarin given baseline covariates mentioned above. By using the estimated PS, we will apply the PS based on the inverse probability of treatment weights (IPTW), where the treatment group of interest will be given a weight of 1/PS, and the comparator group will be given a weight of 1/(1-PS) [4, 5]. The most extreme 1% of PS values (IPTW with trimming) will be excluded to improve comparability between exposure groups.

Main Analysis

- Sociodemographic and clinical characteristics will be summarized with means (STD) or median (IQR) for continuous variables and with count (proportions) for categorical variables for the two treatment comparisons of: apixaban vs warfarin, rivaroxaban vs warfarin, edoxaban vs warfarin and dabigatran vs warfarin (and NOAC vs NOAC, if scientifically feasible).
 - Differences in baseline covariates between users of different OACs will be assessed using the SD where the absolute SD <0.1 will be considered as well balanced.
- The incidence rate of major bleeding overall and by site will be presented as the total number of events per 1,000 person-years, with its 95% CIs estimated using the Poisson distribution.

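### In the written text the Phase II clock starts at the first anticoagulant of any class, heparin included, while the arm is set by an oral drug that, if the Phase I heparin rule carries over, may start up to 14 days later

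*SAP*

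**What the plan says.** **Index date.** SAP 8.2 and Protocol 9.1 give one definition: "The index date will be defined as the date of first prescription for anticoagulants within 30 days after the index VTE event". Inclusion criterion 2 (SAP 8.3.1, Protocol 9.2.1) names UFH and LMWH among the qualifying drugs. Neither place limits the definition to one phase.

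**Phase II follow-up.** SAP 8.4: "Patients will be followed up from the index date to the occurrence of an outcome, treatment discontinuation (30-day grace period), switch to another anticoagulants". Protocol 9.3 has the same rule, ending "switch to another anticoagulants, in-hospital death, or end of the study period (31 Dec 2019) whichever comes first". The outcome is the first major bleed after the index date.

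**Phase II arms.** The exposure list in SAP 8.4 holds only the four NOACs and warfarin. The propensity model in SAP 10 targets the "predicted probability (propensity) of initiating each NOAC compared with warfarin given baseline covariates mentioned above". Tables 13 to 20 label the comparator Warfarin-based, and the note to Figure 1 in SAP 8.1 explains: "Warfarin-based and NOAC-based include either PAC with warfarin/NOAC or warfarin/NOAC only".

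**Heparin lead-in.** Two rules are written, both under Phase I headings. SAP 8.4 says that "a switch from initial heparin treatment to an OAC within 2 weeks after heparin treatment initiation will not be considered a treatment switch". SAP 10 says "we will apply a time restriction of 2 weeks to PAC bridging therapy". The Phase II text neither repeats them nor gives its own definition of a switch.

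**The concern.** A patient who starts heparin on day 0 and warfarin on day 7 has a Phase II clock that starts on heparin. On day 0 nobody can say which arm the patient belongs to; a later prescription decides. That has two consequences.

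- Time on heparin alone, and bleeds during it, are credited to an oral drug not yet taken.
- A patient who bleeds or dies on heparin and never starts an oral drug becomes PAC only and is not in Phase II. The oral arms therefore lose some early bleeds among heparin-first patients, but none among patients who start directly on an oral drug.

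The inverse probability weights are built from covariates at or before the index date, so they cannot undo selection on what happens after it. If heparin-first starts are more common in one arm, the hazard ratio for major bleeding, the Phase II primary result, is shifted.

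**Working it through.** **1. The plan's own figures.** The sample sizes follow from events = (1.960 + 0.842)² / [a(1−a)(ln HR)²] and N = events / event probability. For apixaban versus warfarin, with a = 0.393, HR 0.75 and event probability 1.19%, this gives 397.6 events and N = 397.6/0.0119 ≈ 33,408, against 33,340 stated. All eight stated numbers reproduce within 0.3%. No input concerns the index date or the lead-in, so the point does not touch these figures.

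**2. Four patients under the natural reading (the two-week rules carry over).**

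| Course | Counted in Phase II as |
|---|---|
| Warfarin on day 0, bleed on day 3 | Warfarin-based, event |
| Heparin on day 0, warfarin on day 7, no bleed | Warfarin-based, days 0 to 7 included |
| Heparin on day 0, bleed on day 3, warfarin by day 14 | Warfarin-based, event while on heparin |
| Heparin on day 0, bleed or death on day 3, no oral drug | PAC only, not in Phase II |

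**3. Size.** The documents give none of these inputs, so all are assumptions: s = heparin-first share (sW warfarin, sN NOAC); L = mean lead-in in days; T = mean treatment time in days, counted from the index date; k = share of lead-in bleeders who still start an oral drug and so are counted; r = hazard during the lead-in relative to the hazard on the oral drug.

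With rare events and a true HR of 1.00, an arm's observed rate is proportional to [(T − sL) + sLkr]/T = 1 − sL(1 − kr)/T. Hence

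observed HR = [1 − sN·L(1 − kr)/T] / [1 − sW·L(1 − kr)/T].

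Mid-range case: L = 7, T = 90, k = 0.5, r = 1, so L(1 − kr)/T = 3.5/90 = 0.0389.

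| sW | sN | Observed HR |
|---|---|---|
| 0.50 | 0.25 | 0.9903/0.9806 = 1.010 |
| 0.75 | 0.50 | 0.9806/0.9708 = 1.010 |
| 0.80 | 0.40 | 0.9844/0.9689 = 1.016 |
| 0.75 | 0.25 | 0.9903/0.9708 = 1.020 |
| 0.50 | 0.50 | 1.000 |

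High lead-in hazard: k = 0.8, r = 2, so kr = 1.6 and L(1 − kr)/T = −0.0467. With sW = 0.80 and sN = 0.40, HR = 1.0187/1.0373 = 0.982.

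Wider range: sW of 0.50, 0.75 or 1.00; share difference of 0.25 or 0.50; L of 5, 7 or 10; T of 60, 90 or 180. With k = 0.5 and r = 1 the HR runs from 1.003 to 1.045. With k = 0.8 and r = 2 it runs from 0.952 to 0.996.

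**4. Sign.** By the formula, the direction depends on (sW − sN)(1 − kr). There is no shift if the shares are equal, or if kr = 1 (for example, every lead-in bleeder counted at a constant hazard). Otherwise it can go either way.

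**The case against.** The best defence is that the lead-in is handled. The switch exemption, the bridging limit and the PAC-plus-oral grouping are all written; the grouping note stands under Study design, not Phase I; and the amendment logs say the heparin sentence was revised so that acute heparin is considered for all oral drugs. The mid-range effect is also only 1 to 2%, on assumed inputs. Finally, measuring from first treatment could be a deliberate choice of estimand.

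Much of this stands, and it rules out several stronger readings:

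- *The plan is silent on heparin lead-in.* It is not; the rules are only not restated for Phase II.
- *Heparin-first patients are censored on the day the oral drug starts, so that much oral follow-up is lost.* This uses the PAC-plus-oral grouping to place them in an arm and then drops the exemption that goes with it. The only switch definition in the documents contains the exemption.
- *Heparin-first patients are left out of Phase II altogether.* This conflicts with the Warfarin-based label in the shells.
- *The NOAC columns omit patients bridged with PAC.* SAP 10 defines the NOAC-based group to include PAC/NOAC and stratifies it by drug. Tables 11 and 12 use bare drug names for those strata, so the same names in the Phase II shells most naturally mean the same groups.
- *Table 17 demands follow-up of all oral starters from the oral start.* Its title says neither.
- *The bias could reach 16%.* That needs an event-free lead-in of 14 days in every warfarin patient and no NOAC patient, before 90 oral days: (90 + 14)/90 = 1.156. But SAP 8.4 counts bleeds after the index date, so lead-in bleeds in patients who later start an oral drug do count.

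The estimand defence does not answer the point. A strategy measured from first treatment would need arms that are known at time zero and would have to keep patients who never reach the oral drug. The plan does neither for heparin-first patients.

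**Conclusion.** The point holds and should be fixed before Phase II is run, though the likely effect is small. Even on the natural reading, arm membership for heparin-first patients depends on a prescription up to 14 days after time zero, and those who bleed or die first drop out of the comparison. Weighting on baseline covariates does not repair that.

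Under the mid-range assumptions a true HR of 1.00 is observed as about 1.01 to 1.02. Over the wider ranges it runs from 1.003 to 1.045, or from 0.952 to 0.996 with a doubled lead-in hazard and 80% of lead-in bleeders counted. A reader might infer a bias in a known direction, because Protocol section 7 notes that apixaban and rivaroxaban need no initial parenteral treatment. That suggests the lead-in may differ by comparator, but no shares or lead-in hazards are given, so the sign is open.

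The conclusion rests on text alone. Figures 1 and 2 are not shown and may carry a different Phase II anchor. Their captions and notes define none, and a different anchor would have to be reconciled with SAP 8.2 and 8.3.1.

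**What to change.** For Phase II:

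1. Set time zero at the first oral anticoagulant prescription in every arm, and state the window after VTE diagnosis in which it must fall. Start follow-up and measure covariates at that date.
2. Exclude, in all arms, patients with a major bleed between PAC start and oral start.
3. Keep exclusion 4 anchored on the VTE encounter, as now, so that a lead-in does not disqualify a patient.
4. State that the heparin switch exemption and the PAC/NOAC grouping apply in Phase II.
5. Reconcile exclusion 5 with the PAC-plus-oral groups. Read literally, it removes a patient with heparin and an oral drug on the same day but keeps one whose heparin claim is a day earlier. This is not a strict contradiction, because sequential users can fill those groups, but the text should say whether it covers pairs of oral drugs only.
6. Tabulate heparin-first counts, lead-in days and lead-in bleeds by arm at the Phase I feasibility step, on which Phase II is already conditional.
7. Keep the first-anticoagulant time zero as a sensitivity analysis in Table 20.

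Adjustment for PAC lead-in is optional, as a further sensitivity analysis after checking overlap. If lead-in is closely tied to drug choice, putting it in the propensity model could produce extreme weights.

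Cost: moderate, on the same data extract. It needs a second index date, re-measured covariates, one added exclusion, some Phase I tabulations and a sensitivity row. Text changes fall in Protocol 9.1, 9.2.2, 9.3 and 9.7 and SAP 8.1 to 8.4 and 10, and Figures 1 and 2 need checking. The downside is that lead-in bleeds leave the main Phase II count, and arms may start at different times since VTE diagnosis.
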